4.6 Analysis Sets

4.6.1 Enrolled Set

All participants who agreed to participate in a clinical study after completion of the informed consent process.

4.6.2 Randomized Set

All participants who were randomized to receive a study vaccine

4.6.3 Exposed Set

All participants who received any study vaccination. The allocation in a group is done in function of the administered intervention. The analysis of primary and secondary safety endpoints will be based on this set.

4.6.4 Full Analysis Sets (FASx)

Full Analysis Set 1

- All participants in the Exposed Set who have post-vaccination immunogenicity data at Visit 3 (Day 43). Participants will be analyzed as “randomized” (i.e. according to the vaccine[s] the participant was randomized to receive).

Full Analysis Set 2

- All participants in the Exposed Set who have post-vaccination immunogenicity data at Visit 2 (Day 22). Participants will be analyzed as “randomized” (i.e. according to the vaccine[s] the participant was randomized to receive).

4.6.5 Per Protocol Set (PPSx)

Per Protocol Set 1

- The PPS 1 is a subset of FAS 1. The PPS 1 includes all FAS 1 participants with no major protocol deviations that lead to exclusion at or prior to Visit 3 (Day 43). Primary immunogenicity data will be evaluated based on this set.

Per Protocol Set 2

- The PPS 2 is a subset of FAS 2. The PPS 2 includes all FAS 2 participants with no major protocol deviations that lead to exclusion at or prior to Visit 2 (Day 22). Secondary immunogenicity data will be evaluated based on this set.

Major protocol deviations leading to exclusion are described in Section 5.2 and the Study Deviation Rules document and will be finalized prior to the interim analysis defined in Section 10.2.

4.6.6 Modified Per Protocol Set (mPPSx)

Modified Per Protocol Set 1 (mPPS1)

- *The mPPS 1 is a subset of FAS 1. The mPPS 1 includes all FAS 1 participants with no major protocol deviations (check major protocol deviations definition in [Section 5.2](#)) that lead to exclusion at or prior to Visit 3 (Day 43). The time window between Visit 1 and Visit 2 that is permitted for inclusion in this analysis set is 18-32 days. The time window between Visit 2 and Visit 3 that is permitted for inclusion in this analysis set is 14-32 calendar days.*

All major protocol deviations which lead exclusion from PPS1 will also lead exclusion from mPPS1. Only the major protocol deviations related to sample collection date or vaccination date outside to the intervals described above will not lead exclusion from mPPS1.

Modified Per Protocol Set 2 (mPPS2)

- *The mPPS 2 is a subset of FAS 2. The mPPS 2 includes all FAS 2 participants with no major protocol deviations that lead to exclusion at or prior to Visit 2 (Day 22). The time window between Visit 1 and Visit 2 that is permitted for inclusion in this analysis set is 18-32 days.*

Major protocol deviations leading to exclusion are described in Section 5.2 and the Study Deviation Rules document and will be finalized prior to the interim analysis defined in Section 10.2.

4.6.7 Microneutralization Set

All participants in the Randomized Set who were also selected to the subset of MN evaluation.

4.6.8 Microneutralization Per Protocol Set (MNPPSx)

Microneutralization Per Protocol Set 1

- All participants in the MN Set who are also part of the PPS 1.

Microneutralization Per Protocol Set 2

- All participants in the MN Set who are also part of the PPS 2.

4.6.9 Microneutralization modified Per Protocol Set (MNmPPSx)

Microneutralization modified Per Protocol Set 1

- All participants in the MN Set who are also part of the mPPS 1.

Microneutralization Per Protocol Set 2

- All participants in the MN Set who are also part of the mPPS 2.

5 Participant Disposition

5.1 Disposition

Participant disposition will be summarized as treated for the Exposed Set, and for each study group, age group, and overall. The summary of participant disposition as enrolled will include the number and percentage of participants who were randomized, screen failures, and major reason for screen failure. The summary of participant disposition as treated will include the number of participants in each analysis set defined in Section 4.6, the number and percentage of participants who received any and each study vaccination, the number and percentage of participants who completed the study and the primary reason for withdrawal from the study, the number and percentage of participants who completed the study vaccinations and the primary reason for withdrawal of study vaccination.

Listings will be provided for disposition data based on the Enrolled Set.

5.2 Major Protocol Deviations

A major protocol deviation leading to exclusion is defined as a protocol deviation that is considered to have a significant impact on the immunogenicity results of the participant and will cause a participant to be excluded from the per-protocol analysis sets (PPSx, mPPSx, MN PPSx and MN mPPSx). The number and percentage of participants with each significant protocol deviation leading to exclusion from per-protocol analysis sets will be presented for the Exposed Set, and a listing will also be provided. Major protocol deviations leading to exclusions from PPSx, mPPSx, MN PPSx and MN mPPSx will be summarized by study group, age group, and overall for the Exposed Set.

All protocol deviations will be identified prior to the analysis and a clinical judgment will be necessary to classify each deviation as “major” or “minor”. Key major deviations are provided below, but not limited to:

- Participants enrolled who did not sign the informed consent
- Participants enrolled who signed the wrong informed consent version
- Participants enrolled who included fraudulent data

- Participants enrolled who did not meet entry criteria including age at enrollment
- Participants who received incorrect treatment number
- Participants who were unblinded before end of the study
- Participants incorrectly vaccinated
- Participants who did not receive study vaccinations as planned in protocol
- Participants who did not do the corresponding vaccination visit
- Participants who did not have blood draws as planned in protocol
- Participants with a blood draw outside of allowed time window
- Participants with a vaccination done outside of allowed time window
- Participants who reported taking any prohibited vaccination/therapy as listed in protocol

These key major deviations will be assessed based on the data collected in the eCRFs. The complete list of protocol deviations considered major for this study will be reported in the CSR. If a participant incurs a condition that has the capability of altering their immune response, this will be recorded as an AE and identified as a significant protocol deviation by medical monitoring.

The terms ‘major’ and ‘significant’ for protocol deviations are used interchangeably in study documents and have the same meaning.

Significant protocol deviations leading to exclusion in each of the study populations is described in Table 9.

Table 9 Significant Protocol Deviation that leads in an exclusion

Protocol Deviation	Enr	Rand	Exp	FAS1	FAS2	PPS1	PPS2	mPPS1	mPPS2	MNPPS1	MNPPS2	MNmPPS1	MNmPPS2
Invalid informed consent or fraud in data	X	X	X	X	X	X	X	X	X	X	X	X	X
Incorrect treatment number provided at V2						X		X		X		X	
Unblinding of subject by sponsor/CRO personnel not done per study procedures at V1						X	X	X	X	X	X	X	X
Unblinding of subject by sponsor/CRO personnel not done per study procedures at V2						X		X		X		X	
Investigational vaccine administrated at V1 Day 1 even though subject met exclusion						X	X	X	X	X	X	X	X
Persistent inadequate source documents management after re-education**							X		X		X		X
Vaccine temperature deviation at V1						X	X	X	X	X	X	X	X
Vaccine temperature deviation at V2						X		X		X		X	
Inclusion/Exclusion criteria not meet						X	X	X	X	X	X	X	X
Study vaccine dose not administered according to protocol for V1: Wrong site/route injection/, wrong reconstitution, incorrect volume, Expired vaccine administered						X	X	X	X	X	X	X	X
Study vaccine dose not administered according to protocol for V2: Wrong site/route injection, wrong reconstitution, incorrect volume, Expired vaccine administered						X		X		X		X	

Protocol Deviation	Enr	Rand	Exp	FAS1	FAS2	PPS1	PPS2	mPPS1	mPPS2	MNPPS1	MNPPS2	MNmPPS1	MNmPPS2
Subsequent vaccine administered while contraindicated at V1						X	X	X	X	X	X	X	X
Subsequent vaccine administered while contraindicated at V2						X		X		X		X	
Incomplete treatment course V1						X	X	X	X	X	X	X	X
Incomplete treatment course V2						X		X		X		X	
Vaccination date at V2 done outside of the interval between V1 and V2 of 18-25 Days						X				X			
Vaccination date at V2 done outside of the interval between V1 and V2 of 18-32 Days									X			X	
Serological results collected but not available at V1						X	X	X	X	X	X	X	X
Blood sample at V1: not taken, not available, low serum volume, Lab error (spinning ...), temperature deviation						X	X	X	X	X	X	X	X
Blood sample at V2: not taken, not available, low serum volume, Lab error (spinning ...), temperature deviation					X*		X		X		X		X
Blood sample at V3: not taken, not available, low serum volume, Lab error (spinning ...), temperature deviation				X*		X		X		X		X	
Blood sample collection at V2 done outside of the interval between V1 and V2 of 18-25 Days							X				X		

Protocol Deviation	Enr	Rand	Exp	FAS1	FAS2	PPS1	PPS2	mPPS1	mPPS2	MNPPS1	MNPPS2	MNmPPS1	MNmPPS2
Blood sample collection at V2 done outside of the interval between V1 and V2 of 18-32 Days									X				X
Blood sample collection done at V3 outside of the interval between V2 and V3 of 14 - 32 calendar Days								X				X	
Blood sample collection at V3 done outside of the interval between 38 - 46 Study Days						X				X			
Subjects MN1 and MN2, who were randomized to MN set but were not included										X	X	X	X
Temperature deviations from range defined in protocol and/or SPM for vaccine stored in fridge (0-8C; site level) at V1						X	X	X	X	X	X	X	X

* Subject elimination from FAS 1 or FAS 2 must only take place in cases where blood sample results are not available for any reason above described

** Elimination will be based on case-by-case bases

Enr = Enrolled set; Exp = Exposed set; Rand = Randomized set; FAS = Full Analysis Set; PPS = Per Protocol Set; mPPS = modified Per Protocol Set; MNPPS = Microneutralization per protocol set; MNmPPS = Microneutralization modified per protocol set.

X = Exclusion from the study population set

6 Demographics and Baseline Characteristics

Demographics and baseline characteristics will be summarized for the Exposed Set, Enrolled Set, PPS1, PPS 2, mPPS1, mPPS2, presented by study group, age group, and overall. Participant demographic and baseline characteristics will also be presented in a listing for the Enrolled Set.

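### SAP Table 9 conflicts with SAP 5.2, 4.6.6 and 4.6.9 in three exclusion rows, two of which bear on the primary set PPS1

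*SAP*

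**What the plan says.** SAP 4.6.5 makes PPS1 the set for the primary Day 43 analysis. PPS1 is a subset of FAS 1, and SAP 4.6.4 analyses FAS 1 participants in the group to which they were randomized. SAP 4.6.5 and 4.6.6 place the exclusion rules in Section 5.2 and in a Study Deviation Rules document, which is not among the documents available here. Section 5.2 gives a list of key major deviations and then Table 9, which marks the sets each deviation affects.

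- **Wrong treatment number.** The 5.2 list includes "Participants who received incorrect treatment number", with no visit named. Table 9 has only "Incorrect treatment number provided at V2". The nearest Visit 1 row is "Study vaccine dose not administered according to protocol for V1: Wrong site/route injection/, wrong reconstitution, incorrect volume, Expired vaccine administered", which does not name a wrong kit.
- **Source documents.** The row "Persistent inadequate source documents management after re-education" is marked for PPS2, mPPS2, MNPPS2 and MNmPPS2. Its footnote reads "Elimination will be based on case-by-case bases".
- **Timing of dose 2.** The row "Vaccination date at V2 done outside of the interval between V1 and V2 of 18-32 Days" is marked for mPPS2 and MNmPPS1. The companion row, "Vaccination date at V2 done outside of the interval between V1 and V2 of 18-25 Days", is marked for PPS1 and MNPPS1. SAP 4.6.6 says of mPPS1: "The time window between Visit 1 and Visit 2 that is permitted for inclusion in this analysis set is 18-32 days". SAP 4.6.9 defines MNmPPS1 as the members of the MN Set who are also in mPPS1.

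**The concern.** The primary claim is made formulation by formulation on PPS1. If the programmers follow Table 9, a participant given another group's product at dose 1 is counted in the group to which they were randomized, while the same error at dose 2 leads to exclusion. Data from a participant with persistently poor source records could be dropped from the descriptive Day 22 sets but not from the confirmatory Day 43 sets. The supplementary set mPPS1 would keep participants whom its own definition shuts out. That matters because Protocol Amendment 2 added the modified sets in response to more out-of-window visits than anticipated. If the table is corrected only after treatment codes are open, the choice of who counts could be challenged.

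**Working it through.** **Step 1: read Table 9 by column.** There are 13 set columns, eight of them per-protocol sets.

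| Row | Day 43 sets marked | Day 22 sets marked |
|---|---|---|
| Incorrect treatment number, V2 | PPS1, mPPS1, MNPPS1, MNmPPS1 | none |
| Incorrect treatment number, V1 | no such row | no such row |
| Source documents | none | PPS2, mPPS2, MNPPS2, MNmPPS2 |
| Dose 2 outside 18-25 days | PPS1, MNPPS1 | none |
| Dose 2 outside 18-32 days | MNmPPS1 | mPPS2 |

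**Step 2: compare with the rest of the SAP.**

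- *Treatment number.* Five other deviations have both a V1 and a V2 row: unblinding, vaccine temperature, dose administration, contraindicated vaccination and incomplete course. In each pair the V1 row is marked for all eight per-protocol sets. The fridge-storage row is for V1 only, but the general temperature row covers V2. A V2 row without its V1 partner looks like an omission.
- *Source documents.* Every other row marked only for Day 22 sets concerns the Visit 2 blood sample, where that limit makes sense. Nothing ties source-document quality to Visit 2.
- *Dose 2 outside 18-32 days.* Anyone outside 18-32 days is also outside 18-25 days, so the companion row already removes them from PPS1 and MNPPS1. MNmPPS1 has its own mark. The only Day 43 set that keeps them is mPPS1. Since MNmPPS1 is drawn from mPPS1, the table has the subset excluding people whom the parent set retains for the same reason. On the pattern of the 18-25 row, the marks would fall under mPPS1 and MNmPPS1.
- *Exception sentence in 4.6.6.* It says that timing deviations outside the intervals just described do not lead to exclusion from mPPS1. Those intervals are 18-32 and 14-32 days, so read literally the sentence cancels them.

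**Step 3: reproduce the plan's power (SAP Table 7).** The inputs are n = 57 per formulation and age group and one-sided α = 0.05/12 = 0.417%; the 0.415% printed in Table 7 gives the same cut-offs. The cut-off c is the smallest count whose exact Clopper-Pearson lower limit reaches the threshold, and power is P(Bin(57, p) ≥ c).

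| Criterion | Threshold | Assumed rate | c | Power |
|---|---|---|---|---|
| SCR, 18-64 | 40% | 80% | 34 | 99.99% |
| SPR, 18-64 | 70% | 91% | 50 | 86.26% |
| SCR, ≥65 | 30% | 75% | 28 | >99.99% |
| SPR, ≥65 | 60% | 86% | 45 | 95.12% |

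The product is 82.04%, against 82% stated. The plan's figures reproduce.

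**Step 4: illustrate one retained participant.** Let q be that participant's chance of seroprotection. The documents do not give q, so 0 to 0.7 is shown as an assumed range. The pass probability is q·P(Bin(56, p) ≥ c−1) + (1−q)·P(Bin(56, p) ≥ c).

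- SPR, 18-64: P(Bin(56, 0.91) ≥ 49) = 0.8724 and P(Bin(56, 0.91) ≥ 50) = 0.7633. At q = 0 the result is 76.3%. At q = 0.7 it is 0.7 × 0.8724 + 0.3 × 0.7633 = 84.0%. If the participant is excluded, n = 56, the cut-off is 49 and the result is 87.2%.
- SPR, ≥65: the corresponding figures are 91.5% (q = 0), 94.5% (q = 0.7) and 95.7% (excluded, cut-off 44 of 56).

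**The case against.** The strongest reply is that Table 9 does not decide membership alone. The 5.2 list is open-ended, calls for clinical judgement and, besides the treatment number, names incorrect vaccination with no visit limit; Protocol 9.3.1.1 also names incorrect vaccination. The Study Deviation Rules document may close the gap. This stands in part: on the text, a wrong kit at dose 1 is a major deviation, so the defect is a missing row that conflicts with the text. It does not follow that such participants will remain in PPS1. But text and table give different answers, and the SAP does not say which governs.

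A reader might infer that all three rows leave participants in the Day 43 sets generally. The documents do not support that: the third row affects only mPPS1, whose written definition already imposes the window.

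A reader might also take the source-documents row as a site-wide failure that forces removal. The SAP does not describe it so, and elimination is discretionary. Fraudulent data are excluded from every set by another row. What remains is that the Day 43 columns are left out without explanation.

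Nor does the mark under mPPS2 clearly discard valid Day 22 data. The Day 22 sample and dose 2 belong to the same visit, and a separate row already excludes Visit 2 blood outside 18-32 days from mPPS2. The extra mark is largely redundant.

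Finally, the table was read from a PDF, and a mark displaced by one column could explain the third row. That possibility is open until the original is checked. The first row does not depend on it, because no V1 row exists at all.

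**Conclusion.** The point holds as a conflict within the SAP. Applied as tabulated, Table 9 gives set membership that disagrees with the text for a wrong kit at dose 1 (all eight per-protocol sets, including PPS1) and for dose 2 outside 18-32 days (mPPS1 only). It also limits source-document elimination to the Day 22 sets without a reason, which leaves PPS1 out.

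The size cannot be estimated, because the documents give neither how many participants are affected nor how they respond. The range of 76.3% to about 84%, against 87.2% with exclusion, shows only how sensitive the tightest criterion (seroprotection at 18-64 years) is to one participant who responds less well than planned. It should not be read as an expected loss of power. The direction depends on which product was given: a higher-dose kit in a lower-dose group could push the result upward. The planned sample size and the stated 82% are not in error.

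**What to change.** First check the cell positions in the original PDF. Then, before the Day 43 analysis and its unblinding:

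1. Add a Visit 1 row for an incorrect treatment number, marked for all eight per-protocol sets.
2. Extend the source-documents row to PPS1, mPPS1, MNPPS1 and MNmPPS1. Keep the case-by-case decision, but have it made and recorded by staff without access to treatment codes.
3. In the row for vaccination outside 18-32 days, add the mark under mPPS1. The mark under mPPS2 can be removed, given the Visit 2 blood-sample row.
4. Reword the exception in 4.6.6 so that mPPS1 keeps only timing deviations that fall outside the PPS1 windows but inside 18-32 days (Visit 1 to Visit 2) and 14-32 days (Visit 2 to Visit 3).
5. Bring the Study Deviation Rules document into line with the corrected table.

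The cost is a short SAP edit and a matching change to the deviation programming. PPS1 may lose a few participants.

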6.1 Demographics

The demographic characteristics consist of gender, race, ethnicity, and center. The number and percentage of participants by gender (Male, Female), race (American Indian or Alaska Native, Asian, Black or African American, Native Hawaiian or Other Pacific Islander, White, and Other), ethnicity (Hispanic or Latino, Not Hispanic or Latino) and center, will be reported.

Demographics will be summarized using frequency counts and percentages.

6.2 Baseline Characteristics

The baseline characteristics consist of age (years), age group, baseline height (cm), baseline weight (kg), and baseline body mass index (BMI) (kg/m^2). Age group will be based on the age recorded on the eCRF. BMI is calculated as (body weight in kilograms) / (height in meters)² and will be calculated to 2 decimal places.

Age (years, as recorded on the eCRF), baseline height (cm), baseline weight (kg), and baseline BMI (kg/m^2) will be summarized using descriptive statistics.

Additionally, for web disclosure requirement, the number and percentage of subjects in the following age categories will be presented for the Enrolled Set: 18-64 years, 65-84 years, ≥ 85 years.

6.3 Medical History

Medical history will be coded using the Medical Dictionary for Regulatory Activities (MedDRA), version to be delineated in the CSR. The number and percentage of participants with any medical history will be summarized overall and for each system organ class and preferred term by study group. Percentages will be calculated based on number of participants in the Exposed Set by study group, age group, and overall.

Participant medical history data will also be presented in a listing for the Exposed Set.

6.4 Inclusion and Exclusion Criteria

Participants who did not meet inclusion criteria or met exclusion criteria will be presented in a listing for the Enrolled Set. Inclusion and exclusion criteria are listed in the protocol sections 5.1 and 5.2.

7 Treatments and Medications

7.1 Vaccination History, Concomitant Vaccinations, and Concomitant Medications

All vaccinations and medications will be coded according to the GSK Drug dictionary (GSKDrug), version to be delineated in the CSR. Concomitant medications are also collected for any SAE and pIMD per protocol section 6.5.

7.1.1 Vaccination History and Concomitant Vaccinations

The number and percentage of participants with any prior and concomitant vaccinations recorded on the eCRF will be summarized by study group, age group, and overall. A concomitant vaccination is defined as a vaccination administered in the period starting from the first dose of study vaccine(s) and ending at the last study visit (Day 43). Prior and concomitant vaccinations will be displayed in a listing. All summaries and listings will be performed using the Exposed Set.

7.1.2 Concomitant Medications

Concomitant medications are defined as any medications/products, except vitamins and dietary supplements, associated with an AE administered through EOS.

The number and percentage of participants with at least one concomitant medication will be summarized by study group, age group, and overall and the number and percentage of participants taking each medication will be presented by preferred term. Concomitant medications will be displayed in a listing. All summaries and listings will be performed using the Exposed Set. Participants with missing concomitant medication data will be handled as described in Section 4.5.

7.2 Extent of Exposure

Extent of exposure will be based on the Exposed Set and will be presented by study group, age group, and overall.

7.2.1 Compliance

The number and percentage of participants who received any study vaccination will be presented, as well as the number and percentage of participants who received all expected vaccinations during the study and the number and percentage of participants who withdrew from study vaccine. A participant has withdrawn from study vaccine if vaccination was administered at Visit 1, no vaccination was administered at Visit 2 and the participant has data recorded for at least one of the following: Telephone Contact Day 8 or Visit 2.

In addition, the number and percentage of participants who did not receive all vaccinations with reason (including participants who received a partial vaccination) will be displayed by visit. All study groups and age group are expected to receive 2 vaccinations; one at Visit 1 and one at Visit 2.

